Clinical Study Protocol		
Drug Substance	Goserelin and Bicalutamide	
Study Code	D8664C09827	
Version	5.0	
Date	21 April 2021	

A Multi-centre, Single-arm, Prospective, Interventional Study to Assess Efficacy and Safety of Neoadjuvant Hormone Therapy using Zoladex (Goserelin) and Casodex (Bicalutamide) in Patients with Advanced Prostate Cancer Undergoing Radical Prostatectomy (NARNIA)

Sponsor:

AstraZeneca Investment (China) Co. Ltd, [name]

VERSION HISTORY

Version 1.0, 17 Oct 2017

Version 2.0, 9 Jan 2018

Version 3.0, 7 Jun 2018

Version 4.0, 18 Dec 2019

Version 5.0, 21 Apr 2021

This Clinical Study Protocol has been subject to a peer review according to AstraZeneca Standard procedures. The clinical study protocol is publicly registered and the results are disclosed and/or published according to the AstraZeneca Global Policy on Bioethics and in compliance with prevailing laws and regulations.

PROTOCOL SYNOPSIS

A Multi-centre, Single-arm, Prospective, Interventional Study to Assess Efficacy and Safety of Neoadjuvant Hormone Therapy using Zoladex (Goserelin) and Casodex (Bicalutamide) in Patients with Advanced Prostate Cancer Undergoing Radical Prostatectomy (NARNIA)

National Co-ordinating Investigator

- [name], Peking University First Hospital, Beijing, China
- [name], The Third Affiliated Hospital, Sun Yat-sen University, Guangzhou, China

Study site(s) and number of subjects planned

- Study sites number: 15 sites
- Number of subjects planned: 104 subjects

Study period	Timeline
Estimated date of first subject enrolled	Q1.2021
Estimated date of last subject in	Q4.2021
Estimated date of last subject last visit (LSLV)	Q3. 2022
Estimated date of database lock for whole study	Q4. 2022
Estimated date of CSR	Q1. 2023

Study design

This is a multi-centre, single-arm and prospective study to explore the efficacy and safety of neoadjuvant hormone therapy (NHT) using Zoladex (Goserelin) and Casodex (Bicalutamide) in subjects with advanced prostate cancer undergoing radical prostatectomy (RP). A total of 104 subjects diagnosed with unresectable and locally advanced prostate cancer according to the criteria will be enrolled in the study. The eligible subjects will receive Casodex 50 mg orally per day in combination with Zoladex 10.8 mg implant subcutaneously per 12 weeks for 24 weeks. The subjects will undergo a RP [RALP (robot-assisted laparoscopic prostatectomy),

laparoscopic RP or RRP (radical retropubic prostatectomy)] plus extended pelvic lymph node dissection (ePLND) thereafter if the primary tumour is assessed as resectable. Subjects will be prescribed post-surgical treatment such as continuous androgen deprivation therapy (ADT) and metastasis-directed therapy upon investigator's discretion and be followed-up for up to 3 months to evaluate the postoperative complications and the decrease of PSA.

Objectives

Primary Objective:	Outcome Measure:
To evaluate the efficacy of neoadjuvant hormonal therapy in the subjects with locally advanced prostate cancer through the rate of radical resection following neoadjuvant hormonal therapy (NHT)	Actual radical prostatectomy rate

Secondary Objectives:	Outcome Measures:
To investigate the efficacy of NHT before RP in subjects with locally advanced prostate	The mean PSA at the end of NHT and PSA change from baseline
cancer by assessment of PSA, percentage of positive surgical margin for primary tumour, incidence of seminal vesicle invasion and involvement of pelvic lymph nodes	Percentage of positive surgical margin for primary tumour (A positive surgical margin is defined as the presence of cancer at the inked margin of resection in an RP specimen)
	Incidence of seminal vesicle invasion and involvement of pelvic lymph nodes
	Pathological downstaging rate
	Rate of post surgical PSA decreased to less than 0.1ng/ml
To observe surgical-related variables and complications	Operative duration, intraoperative estimated blood loss, duration of indwelling catheterization, complications, time to continence and urinary continence rate at 12 weeks, potent rates in erectile function at 12 weeks after surgery
To evaluate the safety of NHT using goserelin and bicalutamide	AEs/SAEs

Exploratory Objective:	Outcome Measure:	
Occurrence of homologous recombination repair gene mutation (HRRm) in the patients with locally advanced prostate cancer	Incidence of tumor tissue and germline homologous recombination repair gene mutation	

Target treatment subject population

Subjects who are diagnosed with unresectable and locally advanced prostate cancer according to the criteria at clinical stage of T3 and T4 are the target population of this study.

(Definition of resectability: clear lateral border of prostate in digital rectal examination, and clear bladder neck with no invasion in radiological examination or cystoscopy, no invasion of urethra or external sphincter at the apex of prostate; non-resectable will be considered if the above definition is not met)

Planned duration of treatment

The treatment duration of study will be 24 weeks and the follow-up period will be 3 months.

The eligible subjects will receive Casodex 50 mg orally per day in combination with Zoladex 10.8 mg implant subcutaneously as neoadjuvant therapy per 12 weeks for up to 24 weeks. Then the subjects will receive radical prostatectomy if the subjects are assessed as having a resectable primary tumour. Subjects will be followed-up for up to 3 months after RP.. The reason for failure to operate will be collected for the subjects who actually can not receive radical prostatectomy following NHT.

Investigational product, dosage and mode of administration

Investigational products are Zoladex[®] (goserelin acetate implant) 10.8mg and Casodex[®] (bicalutamide) 50 mg.

- Zoladex[®] (goserelin acetate implant) 10.8 mg should be administered subcutaneously every 12 weeks into anterior abdominal wall below the navel line.
- Casodex[®] (bicalutamide) 50 mg should be taken orally once per day.

Statistical methods

The primary endpoint is the actual radical prostatectomy rate. An approximate sample size of 104 subjects provides a precision of 6.1% based on the bilateral 95% confidence interval (CI) for the resectability rate of 90% assuming a dropout rate of 10% (half width of 95% CI).

Data will be summarized using descriptive statistics as appropriate. Continuous variables will be summarised by the number of observations (n), mean (or geometric mean as appropriate), standard deviation (SD), median, quartiles (Q1 and Q3), minimum, and maximum. Categorical variables will be summarised by frequency counts and percentages for each category. The 95% CI will be provided when appropriate.

TABLE OF CONTENTS

PAGE

TITLE PA	GE	1	
VERSION HISTORY			
PROTOCO	DL SYNOPSIS	3	
TABLE OF	F CONTENTS	6	
1	INTRODUCTION	13	
1.1	Background and rationale for conducting this study		
1.2	Rationale for study design and doses	14	
1.3	Benefit/risk and ethical assessment	14	
1.4	Study design	14	
2	STUDY OBJECTIVES	17	
2.1	Primary objective	17	
2.2	Secondary objectives	17	
2.3	Exploratory objective	17	

Abbreviation or special term	Explanation						
GMP	Good Manufacturing Practice						
Hb	Haemoglobin						
HIV	Human Immunodeficiency Virus						
HL	Hy's Law						
HRR	Homologous recombination repair						
HRRm	Homologous recombination repair mutation						
g-HRRm	Germline homologous recombination repair mutation						
t-HRRm	Tumor tissue homologous recombination repair mutation						
ICH	International Conference on Harmonisation						
IHC	Immunohistochemistry						
LHRH	Luteinizing Hormone-releasing Hormone						
IMP	Investigational Medicinal Product						
IP	Investigational Product						
LSLV	Last Subject Last Visit						
IVRS	Interactive Voice Response System						
IWRS	Interactive Web Response System						
MedDRA	Medical Dictionary for Regulatory Activities						
MRI	Magnetic Resonance Imaging						
NHT	Neoadjuvant Hormone Therapy						
OS	Overall Survival						
PFS	Progression Free Survival						
PHL	Potential Hy's Law						
PI	Principal Investigator						
PSA	Prostate Specific Antigen						
RALP	Robot-assisted Laparoscopic Prostatectomy						
RP	Radical Prostatectomy						
RPAS	RP Analysis Set						
RRP	Radical Retropubic Prostatectomy						
SAE	Serious Adverse Event						
SAP	Statistical Analysis Plan						
SD	Standard Deviation						

Abbreviation or special term	Explanation
TBL	Total Bilirubin
ULN	Upper Limit of Normal

1 INTRODUCTION

1.1 Background and rationale for conducting this study

The clinical neoadjuvant hormonal therapy (NHT) for local prostate cancer includes androgen deprivation therapy prior to radiotherapy or surgery, usually using the therapeutic regimen of luteinizing hormone releasing hormone agonist alone or combined with anti-androgens. The rational for this approach is based on the assumption that NHT will reduce both the tumour and normal prostatic tissue volume, and induce cancer regression by the mechanism of apoptosis ^[6].

A series of clinical trials on neoadjuvant hormonal therapy since the early 1990s have demonstrated that NHT could reduce the positive rate of surgical margin after radical prostatectomy and down-stage the tumor, however, these studies are usually small and mainly enroll the patients with low risks or local prostate cancer, and are unable to show a more significant survival benefit in the patients with locally advanced prostate cancer receiving NHT versus those not receiving the treatment. Therefore, neoadjuvant hormonal therapy has not been recommended as the standard of care in the guideline for the patients with locally advanced prostate cancer before radical prostatectomy ^[7-13]. Some latest studies on neoadjuvant hormonal therapy have shown that 6-month neoadjuvant hormonal therapy prior to radical prostatectomy could better control local lesions and more effectively reduce the positive rate of surgical margin and PSA recurrence rate ^[14-17]. At the same time, the radiological study has also demonstrated a better efficacy of 6-month NHT than 1- or 3-month therapy ^[18].

Homologous recombination repair mutation (HRRm) is one common gene mutation in prostate cancer, including germline mutation and somatic cell line mutation. It has been shown in the study that HRRm was related with high-grade prostate cancer, and the prognosis was poor in the patients with prostate cancer with HRRm ^[19-20]. It has been shown in one small study that the incidence of germline HRRm was about 8.7% in locally advanced prostate cancer in China, however, there was lack of related study data on the incidence of tumor tissue HRRm ^[21].

This study is proposed primarily to observe the efficacy and safety of 24-week NHT (Zoladex and Casodex) in patients with locally advanced or oligometastatic prostate cancer. Patients will be followed up for three months after RP following NHT, as to evaluate surgery associated complications and the rate of subjects with postoperative PSA decrease to <0.1ng/ml. At the

same time, the occurrence of HRR mutation will also be explored in Chinese patients with locally advanced prostate cancer in this study.

1.2 Rationale for study design and doses

The purpose of this study is to assess the efficacy and safety of Casodex 50 mg daily in combination with Zoladex 10.8 mg implant subcutaneously every 12-weeks for 24 weeks as neoadjuvant hormonal treatment in patients with locally advanced prostate cancer.

A single-arm, prospective study is designed to enrol 104 with locally advanced prostate cancer. NHT may downstage the primary tumour and improve the surgical margin status and resectability rate of the primary tumour. The surgical efficacy and complications will be followed up for three months after RP following NHT.

Subjects will receive 24-weeks of treatment with Casodex 50 mg and Zoladex 10.8 mg implant, which have been launched in China.

1.3 Benefit/risk and ethical assessment

Casodex 50 mg daily in combination with Zoladex 3.6 mg or 10.8 mg implant are standard therapy as CAB in subjects with advanced prostate cancer. Subjects with neoadjuvant hormonal therapy are anticipated to improve the resectability of the primary tumour and reduce the proportion of positive surgical margins. Those improvements may providelonger survival benefit. The toxicities of Casodex and Zoladex are well understood and well manageable.

1.4 Study design

This is a multi-centre, single-arm and prospective study to explore the efficacy and safety of neoadjuvant hormone therapy (NHT) for advanced prostate cancer patients undergoing radical prostatectomy (RP). A total of 104 subjects with locally advanced prostate cancer at clinical stage of T3 and T4 (N0 or N1) will be enrolled at almost 15 centres in China.

The eligible subjects will receive Casodex 50 mg orally per day in combination with Zoladex 10.8 mg implant subcutaneously every 12 weeks as neoadjuvant therapy for 24 weeks, and then will be assessed for resectability of the primary tumour. The subjects will undergo a RP [RALP (robot-assisted laparoscopic prostatectomy), laparoscopic RP or RRP (radical retropubic prostatectomy)] plus ePLND thereafter if the primary tumour is assessed as resectable. Surgical margin status and involvement of pelvic lymph nodes will be evaluated. Subjects will be prescribed post-surgical treatment such as continuous ADT and metastasis-directed therapy upon investigator's discretion and be followed-up for up to 3 months. The reason for failure to operate will be collected for the patients who actually can not receive radical prostatectomy following NHT.

The subjects will return for all regular clinical visits and perform all scheduled assessments until the end of study.

Figure 1 Study flow chart

Definition of resectability: clear lateral border of prostate in digital rectal examination, and clear bladder neck with a in radiological examination or cystoscopy, no invasion of urethra or external sphincter at the apex of prostate

16 (57)

2 STUDY OBJECTIVES

2.1 Primary objective

Primary Objective:	Outcome Measure:
To evaluate the efficacy of neoadjuvant hormonal therapy in the subjects with locally advanced prostate cancer through the rate of radical resection following neoadjuvant hormonal therapy (NHT)	Actual radical prostatectomy rate

2.2 Secondary objectives

Secondary Objectives:	Outcome Measures:		
To investigate the efficacy of NHT before RP in subjects with locally advanced prostate cancer	The mean PSA-at the end of NHT and PSA change from baseline		
by assessment of PSA, percentage of positive surgical margin for primary tumour, incidence of seminal vesicle invasion and involvement of pelvic lymph nodes	Percentage of positive surgical margin for primary tumour (A positive surgical margin is defined as the presence of cancer at the inked margin of resection in an RP specimen)		
	Incidence of seminal vesicle invasion and involvement of pelvic lymph nodes		
	Pathological downstaging rate		
	Rate of subjects with post-surgical PSA decreased to less than 0.1 ng/mL		
To observe surgical-related variables and complications	Operative duration, intraoperative estimated blood loss, duration of indwelling catheterization, complications, time to continence and urinary continence rate at 12 weeks, potent rates in erectile function at 12 weeks after surgery		
To evaluate the safety of NHT using goserelin and bicalutamide	AEs/SAEs		

2.3 Exploratory objective

Exploratory Objective:	Outcome Measure:
Occurrence of homologous recombination repair gene mutation (HRRm) in the patients with locally advanced prostate cancer	Incidence of postoperative tumor tissue and germline homologous recombination repair gene mutation

3

SUBJECT SELECTION, ENROLMENT, RESTRICTIONS, DISCONTINUATION AND WITHDRAWAL

Each subject should meet all of the inclusion criteria and none of the exclusion criteria for this study. Under no circumstances can there be exceptions to this rule.

3.1 Inclusion criteria

For inclusion in the study, subjects should fulfil the following criteria:

- 1. Provision of informed consent prior to any study procedures
- 2. Male subjects
- 3. Age between 18 and 80 (including 18 and 80)
- 4. ECOG performance status 0-1
- 5. Histologic confirmation of prostate adenocarcinoma
- 6. Documented evidence of clinical stage T3 and T4 (N0 or N1)
- 7. Not meeting the criteria on resectability. Resectability is defined as clear lateral border of prostate in digital rectal examination, and clear bladder neck with no invasion in radiological examination or cystoscopy, no invasion of urethra or external sphincter at the apex of prostate.
- 8. Subject has not received local therapy for the primary lesion of prostate cancer and no contraindication for radical prostatectomy
- 9. Male subjects must be surgically sterile or using an acceptable method of contraception (defined as barrier methods in conjunction with spermicides) for the duration of the study (from the time they sign consent) and for 3 months after the last dose of study drugs to prevent pregnancy in a partner
- 10. Subjects who are blood donors should not donate blood during the study and for 3 months following their last dose of study drugs
- 11. Subjects are willing and able to comply with the protocol for the duration of the study including undergoing treatment and scheduled visits and examinations.

3.2 Exclusion criteria

Subjects should not be enrolled in the study if any of the following exclusion criteria are fulfilled:

1. Staff involved in the planning and/or conduct of the study (applies to both AstraZeneca staff and/or staff at the study site)

- 2. Previous enrolment in the present study
- 3. Participation in another clinical study with an investigational product (IP) during the last one month
- 4. Previous treatment with surgical castration or chemotherapy
- 5. Previous treatment with PARP inhibitor
- 6. Subjects with a known hypersensitivity to Zoladex[®] (goserelin acetate implant) / Casodex[®] (bicalutamide) or any of the excipients of the products
- 7. Psychiatric or medical conditions which, in the opinion of the investigator, would not allow the subject to undergo the proposed treatments safely
- 8. Any laboratory abnormalities, which in the opinion of the investigator (especially for subjects with moderate to severe hepatic impairment), may put the subject at risk if participating in the study
- 9. Persistent toxicities (>CTCAE grade 2) caused by previous cancer therapy, excluding alopecia
- 10. Subjects with known active hepatitis (i.e. Hepatitis B or C) due to risk of transmitting the infection through blood or other body fluids
- 11. Immunocompromised subjects, e.g., subjects who are known to be serologically positive for human immunodeficiency virus (HIV)
- 12. Unwilling or unable to comply with protocol requirements and scheduled visits

Procedures for withdrawal of incorrectly enrolled subjects see Section 3.4.

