7.7 Concomitant and other treatments

Prohibited Medication/Class of Drug:	Usage:
Other LHRH agonists include, not limited to: triptorelin / leuprorelin	Not permitted to be used before RP
Other antiandrogens include, not limited to: flutamide / nilutamide	Not permitted to be used before RP

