4.3.4 Medications and Procedures

The Medications will be presented and coded using WHODrug Global March 1, 2020 or higher version.

See Appendix 1 for handling of partial dates for medications, in the case where it is not possible to define a medication as prior, concomitant, or post treatment, the medication will be classified by the most conersativez case; i.e. concomitant.

- 'Prior' medications are medications which started and stopped prior to the first dose of study medication.
- 'Concomitant' medications are medications which:
 - o started prior to, on or after the first dose of study medication but no later than the end of study medication,
 - AND ended on or after the date of first dose of study medication or were ongoing at the end of the treatment.
- 'Post' medications are medications which started after the end of study medication.

Prior, Concomitant and Post Medications will be listed individually for each subject. The number and percentage of subjects using each medication will be displayed together with the number and percentage of subjects using at least one medication within each therapeutic class (ATC-Level 2) and generic term.

Prior and concomitant Procedures will also be listed individually for each subject. The number and percentage of subjects using each procedure will be displayed together with the number and percentage of subjects using at least one procedures.

Previous/current cancer therapy and previous/current radiotherapy will be summarized using same method as described above.

Above analyses will be performed based on FAS.

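### Eligibility does not exclude earlier medical androgen deprivation; if pretreated men enter, the PSA fall is understated and the RP rate does not reflect 24 weeks of NHT alone

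*Protocol*

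**What the plan says.** Protocol 3.1 and 3.2 address earlier treatment in five places:

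- Exclusion 4 bars "Previous treatment with surgical castration or chemotherapy".
- Exclusion 5 bars an earlier PARP inhibitor.
- Inclusion 8 requires "Subject has not received local therapy for the primary lesion of prostate cancer and no contraindication for radical prostatectomy".
- Exclusion 9 bars "Persistent toxicities (>CTCAE grade 2) caused by previous cancer therapy, excluding alopecia", which takes for granted that some men have had cancer therapy.
- Inclusion 7 requires every man to be unresectable at entry: "Not meeting the criteria on resectability".

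Protocol 7.7, on concomitant treatment, has two rows: "Other LHRH agonists include, not limited to: triptorelin / leuprorelin" and "Other antiandrogens include, not limited to: flutamide / nilutamide". Both carry the rule "Not permitted to be used before RP", with no start point.

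Testosterone and PSA are measured at screening (Protocol 4.1, 4.2), but neither has an eligibility threshold. SAP 3.2 takes PSA change from the enrolment value. SAP 3.1 counts RP after NHT over all FAS subjects. SAP 4.3.4 says "Previous/current cancer therapy and previous/current radiotherapy will be summarized using same method as described above". The SAP plans no subgroup or sensitivity analysis by earlier hormone therapy.

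**The concern.** The study sets out to describe 24 weeks of goserelin plus bicalutamide before surgery. Exclusion 4 names surgical castration and does not mention medical castration. A man who earlier received goserelin or bicalutamide, and is still unresectable, meets every written criterion on treatment history.

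If such men enter, two things follow. Their enrolment PSA may already be low, so the change from baseline captures only the remaining part of the fall. Their total hormone exposure before surgery also exceeds 24 weeks, so RP, margin status and downstaging cannot be credited to the 24-week course alone. With one arm, no comparator cancels either effect, and the SAP has no analysis that would separate these men.

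A related, secondary gap is that 7.7 does not mention chemotherapy or radiotherapy between Day 1 and RP. An RP that followed such therapy would still count as a success.

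**Working it through.** **Which earlier treatments are barred**

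| Earlier treatment | Rule | Barred? |
|---|---|---|
| Surgical castration, chemotherapy | Exclusion 4 | Yes |
| PARP inhibitor | Exclusion 5 | Yes |
| Local therapy to the primary | Inclusion 8 | Yes |
| Other LHRH agonist or other antiandrogen | 7.7, before RP, no start point | Arguably, if still active at entry; not clearly, if finished |
| Goserelin or bicalutamide, finished before Day 1 | None | No |
| LHRH antagonist | None | No |

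**The plan's own figure.** Protocol 8.2 gives 104 subjects and a 6.1% half-width at a 90% rate with 10% dropout. The Wald formula gives n = 0.90 × 0.10 × (1.96/0.061)² = 92.9, so 93 evaluable; 93/0.9 = 103.3, so 104. The figure reproduces, is not in dispute, and serves below as a yardstick.

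**RP rate.** The documents give neither the share f of pretreated men nor the gap between their RP rate and that of untreated men, so both are assumptions. With 90% in untreated men, observed rate = 0.90 + f × gap. A gap of +10 points is the ceiling, since it means every pretreated man has RP.

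| f | Gap −20 points | Gap +10 points |
|---|---|---|
| 10% | 88% | 91% |
| 20% | 86% | 92% |
| 30% | 84% | 93% |

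The shift is 2 to 6 points down or 1 to 3 points up.

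**PSA change.** Assume a share f had already achieved a fraction g of their PSA fall before enrolment. Mean change, relative to that in untreated men, is 1 − f × g.

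| f | g = 0.5 | g = 0.9 |
|---|---|---|
| 10% | 0.95 | 0.91 |
| 20% | 0.90 | 0.82 |
| 30% | 0.85 | 0.73 |

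Here the direction is fixed: the fall is understated.

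**Precision if pretreated men are set aside.** Starting from 94 evaluable men (104 × 0.9 = 93.6), 85, 75 or 66 remain at f = 10%, 20% or 30%. The Wald half-width is then 6.4%, 6.8% or 7.2%.

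**The case against.** The case on the other side is substantial.

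- The gap is narrower than exclusion 4 alone suggests. A man with an active depot of another LHRH agonist arguably fails through 7.7 together with exclusion 12, which requires ability to comply with the protocol. Protocol 7.2 has the two study drugs starting together, and 6.7 classes Zoladex above 10.8 mg per 12 weeks as an overdose; both fit badly with overlapping earlier treatment. This stands. It leaves non-overlapping goserelin or bicalutamide, LHRH antagonists, and, because 7.7 has no start point, some doubt about other agents already finished.
- Inclusion 7 keeps out a man whom earlier therapy has already made resectable. This stands. It limits upward bias in the RP rate and may select poor responders.
- Prior medications are listed and earlier cancer therapy is tabulated, so pretreated men can be seen. This stands, but a listing does not show what the endpoints would be without them.
- The tabulation of current cancer therapy in SAP 4.3.4 might be read as expecting chemotherapy or radiotherapy before surgery. It is only a table heading and could cover treatment after RP. What remains is that no rule handles the case before RP.

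A reader might also infer that the trial tests length of exposure, because Protocol 1.1 cites better results with 6 months than with 1 or 3. It does not: there is one arm, one duration and a descriptive analysis. That passage only motivates the choice of 24 weeks.

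**Conclusion.** The concern holds in conditional form. The criteria do not exclude earlier medical androgen deprivation, and 7.7 closes only part of the gap. If pretreated men enter, the PSA fall is understated, and the RP, margin and downstaging rates do not reflect 24 weeks of NHT alone.

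Three stronger readings are tempting and unsupported:

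- That neither the RP rate nor the PSA change can be the effect of 24 weeks of NHT. This requires pretreated men to enter in material numbers, and the documents give no share.
- That the RP rate will be inflated. The direction is not determined, for the reason given by inclusion 7.
- That 5 to 20 points of the RP rate are at stake if 5% to 20% of men are pretreated (5 to 21 men, each 1/104 = 0.96 points). That is a headcount, not a bias: a pretreated man distorts the rate only if his outcome would otherwise have differed. Starting from 94/104 = 90.4%, removing one success gives 93/103 = 90.3%, and removing one failure gives 94/103 = 91.3%.

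Under the assumed shares and gaps, the shift in the RP rate is 1 to 6 points, at its extreme about as large as the planned half-width. The PSA part is firmer in direction, but its size also rests on assumptions. This is a worthwhile and inexpensive improvement; it does not invalidate the design.

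**What to change.** 1. **Protocol 3.2.** Extend exclusion 4 to earlier medical androgen deprivation or antiandrogen therapy for prostate cancer, naming LHRH agonists, LHRH antagonists and antiandrogens, and including goserelin and bicalutamide. Reconcile 7.7 with it and give 7.7 a start point.
2. **SAP 4.3.6 and 4.3.7.1.** For men already enrolled, flag earlier hormone therapy and report the primary rate and PSA change with and without them. Base the flag on a start date before first study dose, from the medication records: SAP 4.3.4 classes a drug still being taken at first dose as concomitant, so the prior category alone would miss it.
3. **Secondary point, SAP 4.3.6.** Add a supportive primary rate in which RP after other anticancer therapy given between Day 1 and RP is not counted as a success.

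The cost is one eligibility line and a few supportive tables from medication data already collected. Protocol 8.1 allows SAP amendments until data lock. Recruitment may slow slightly. First enrolment was estimated for Q1 2021 and protocol version 5.0 is dated April 2021, so a change may arrive mid-enrolment and create two eligibility populations; the with-and-without tables deal with that. The tables that leave out pretreated men will have somewhat wider intervals, as shown in the working.
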